**Data Handling and Record Keeping**

This study is to be conducted according to US and international standards of Good Clinical Practice (FDA Title 21 part 312 and International Conference on Harmonization guidelines), applicable government regulations and Institutional research policies and procedures. This protocol and any amendments will be submitted to a properly constituted independent Institutional Review Board (IRB), for formal approval of the study conduct. Information about study subjects will be kept confidential and managed according to the requirements of the Health Insurance Portability and Accountability Act of 1996 (HIPAA). Those regulations require a signed subject authorization informing the subject of the following: 1) What protected health information (PHI) will be collected from subjects in this study 2) Who will have access to that information and why 3) Who will use or disclose that information 4) The rights of a research subject to revoke their authorization for use of their PHI. All subjects for this study will be provided with a printed consent form describing this study and providing sufficient information for subjects to make an informed decision about their participation in this study. This consent form will be submitted with the protocol for review and approval by the IRB for the study. The formal consent of a subject, using the IRB-approved consent form, will be obtained before the subject is submitted to any study procedures. This consent form will be signed by the subject and the investigator-designated research professional obtaining the consent. The subject will be given a signed copy of the informed consent for their records. After study initiation, the electronic case report form (eCRF) will be the primary data collection instrument for the study. Only the study staff will have access to this password protected file. No subject identifiers will be included in the eCRF and electronic databases that are used to record clinical data on participants. All clinical data will be kept completely confidential. The PI, [name] and the Co-Is Drs. [name] and [name] or their designees will be responsible for the clinical data management.

**PROVISIONS TO MONITOR THE DATA TO ENSURE THE SAFETY OF PARTICIPANTS:**

**Safety:**

Safety Endpoints: The primary safety endpoints will be assessed on the AEs and SAEs that are observed throughout the trial. For the purpose of this clinical trial, the National Cancer Institute Common Terminology Criteria for Adverse Events v4.0 3(CTCAE), dated June 14,

*Northwestern University Feinberg School of Medicine:* Extended-Release Tacrolimus Vs. Twice-Daily Tacrolimus

2010, will be used to grade all adverse events. The collection of AE's and SAE's is limited in this study to those Grade 3 or higher that are related to study mandated procedures.

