### **Recording of Adverse Events**

At each contact with the subject, the investigator/member of investigator's team will seek information on adverse events by specific questioning and, as appropriate, by examination. Information on all adverse events will be recorded in the source document. All clearly related signs, symptoms, and abnormal diagnostic procedures results should be recorded in the source document, though should be grouped under one diagnosis.

All adverse events occurring during the study period that meet the criteria above will be recorded. The clinical course of each event should be followed until resolution, stabilization, or until it has been determined that the study treatment or participation is not the cause. Serious adverse events that are still ongoing at the end of the study period must be followed up to determine the final outcome. Any serious adverse event that occurs after the study period and is considered to be possibly related to the study treatment or study participation will be recorded and reported according to IRB requirements.

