### **RISKS TO PARTICIPANTS:**

The risks to the subjects are limited to the risks related to venipuncture and at least two passes of renal biopsies. Also, the routine risk of rejection with either of the drugs is expected; in fact, lower risk of nephrotoxicity is anticipated with LCP-Tacro/Envvarsus® XR.

*Northwestern University Feinberg School of Medicine:* Extended-Release Tacrolimus Vs. Twice-Daily Tacrolimus

The National Cancer Institute Common Terminology Criteria for Adverse Events v4.03 (CTCAE), dated June 14, 2010 will be used to grade all adverse (either serious or non-serious) events. It is the responsibility of the Principal Investigator to oversee the safety of the study. This safety monitoring will include careful assessment and appropriate reporting of adverse events as noted above. Medical monitoring will include a regular assessment of the number and type of serious adverse events. Information on all adverse events (signs, symptoms, abnormal diagnostic procedures, treatments) will be recorded in the appropriate adverse event module of the case report form (CRF). The clinical course of each event will be followed until resolution, stabilization, or until it has been determined that the study participation is not the cause. Serious adverse events that are still ongoing at the end of the study period will be followed to determine the final outcome.

Serious adverse events that are determined to be unexpected and at least possibly related to study participation will be submitted to the IRB within 5 business days of the investigator's knowledge of the event. Follow-up information will be submitted to the IRB as required. The IRB/Office for the Protection of Research Subjects at NU is under the direction of [name], MS, CIP, CHRC, [name].

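### The plan gives two incompatible rules for which adverse events enter the study record, and the narrower one turns on an undefined term, so the content of the primary safety endpoint is unsettled

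*Combined protocol and SAP*

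**What the plan says.** Three sections of the combined protocol and SAP bear on which AEs are collected.

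- **Safety** (under Provisions to Monitor the Data). The endpoint is stated without limit: "The primary safety endpoints will be assessed on the AEs and SAEs that are observed throughout the trial". The CTCAE scale "will be used to grade all adverse events". The section then narrows collection: "The collection of AE's and SAE's is limited in this study to those Grade 3 or higher that are related to study mandated procedures".
- **The next section, Recording of Adverse Events.** Staff ask about AEs at each contact, and "Information on all adverse events will be recorded in the source document". The next paragraph applies the limit: "All adverse events occurring during the study period that meet the criteria above will be recorded". For an SAE arising after the study period, the test is different: one that "is considered to be possibly related to the study treatment or study participation will be recorded and reported according to IRB requirements".
- **Risks to Participants.** "Information on all adverse events (signs, symptoms, abnormal diagnostic procedures, treatments) will be recorded in the appropriate adverse event module" of the CRF. There is no grade or relatedness condition. SAEs that are "unexpected and at least possibly related to study participation will be submitted to the IRB within 5 business days". The section also provides for regular assessment of the number and type of SAEs.

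Data Handling and Record Keeping makes the electronic CRF the main instrument for collecting data. The Statistical analysis section names no AE endpoint and no AE analysis.

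**The concern.** The endpoint, the collection limit and the CRF instruction cannot all be followed. Two coordinators each working faithfully from the protocol could build different safety datasets.

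This is a randomised, open-label comparison of two tacrolimus formulations. Under the narrow rule an event must be judged related to a study-mandated procedure before it is collected. If taking the drug is not a procedure, the AE endpoint leaves out events attributed to the treatments being compared. Infections not attributed to a procedure would also be missing. The Stopping Rules section treats post-transplant infections as AEs, expects fewer in the experimental arm, and allows them to end participation; the CRF data could not then show whether that expectation was met. Because arm is known when relatedness is judged, using that judgement as an entry condition also leaves room for different capture in the two arms. That is a possibility, not something the documents show.

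**Working it through.** No arithmetic applies: the plan states no AE rate and no figure that depends on AE scope. The check is a comparison of the text.

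**Step 1. Can the sections be read together?** Two readings were tried.

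- *Source documents hold everything, the CRF holds the filtered set.* This fits Safety and Recording of Adverse Events. It fails at Risks to Participants, which names the CRF and says all events. I take that CRF to be the electronic CRF of Data Handling and Record Keeping.
- *Risks to Participants imports the limit by referring back to what was noted above.* That back-reference attaches to assessing and reporting AEs. The CRF sentence comes later and carries no limit.

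Neither reading removes the conflict.

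**Step 2. Is the filter defined?** The term study mandated procedures occurs once, in Safety. The surrounding text does not settle it:

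- Risks to Participants names venipuncture and renal biopsy as the risks, but then mentions rejection risk with either drug.
- Secondary endpoints makes the month 3 and month 12 biopsies standard of care, so even these may not be study-mandated.
- Study Drugs says the sponsor supplies none of the drugs, while the heading for the once-daily product calls it study-related.
- Recording of Adverse Events follows events until the study treatment or participation is ruled out as the cause, which is wider than procedures.

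**Step 3. What enters the CRF under each reading?**

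| Event | Risks to Participants governs | Safety governs, drug counts as a procedure | Safety governs, drug does not count |
|---|---|---|---|
| Grade 1-2, any cause | in | out | out |
| Grade 3+, attributed to a research blood draw | in | in | in |
| Grade 3+, attributed to a standard-of-care biopsy | in | unclear | unclear |
| Grade 3+, attributed to the tacrolimus formulation (including infection) | in | in | out |
| Grade 3+ infection attributed to neither drug nor procedure | in | out | out |

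The limit is written for AEs and SAEs alike, so seriousness alone does not bring an event in.

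**Step 4. What is captured whatever the reading?** All AEs are in source documents. Unexpected SAEs possibly related to participation go to the IRB, and SAE number and type are regularly assessed. Urinary injury markers are a primary endpoint. Biopsy evidence of calcineurin-inhibitor toxicity, donor-specific antibody, rejection, graft loss and death are secondary endpoints. None of these depends on the AE rule.

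**The case against.** The strongest case on the other side is that this is a narrow wording inconsistency in a 50-patient pilot with no specified AE analysis. Limited AE collection is a legitimate choice, and the Safety section makes it explicitly. The infection expectation is an aside in a stopping rule; infection is not an objective, an endpoint or part of the hypothesis. Most of this stands. It confines the consequence to descriptive reporting, and it means the choice of rule belongs to the sponsor and investigator. It does not remove the contradiction, because the same protocol also instructs staff to enter all AEs in the CRF.

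A reader might infer more than the documents support:

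- *That the excluded events are lost or go unmonitored.* They are kept in source documents and could be abstracted by arm, and SAEs are reviewed regularly. They would be absent from the CRF dataset, not from all records.
- *That nephrotoxicity or graft outcomes would be missed.* These have their own endpoints.
- *That grading is also contradictory.* It is not: Safety and Risks to Participants both grade all AEs.
- *That in-study SAEs are handled less strictly than later ones across the board.* Unexpected, possibly related in-study SAEs still reach the IRB, so any asymmetry concerns the study record and expected SAEs.
- *That small-sample bounds or exact tests at 25 per arm show the size of the harm.* Such figures describe the sample size under any collection rule and do not measure this defect.

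**Conclusion.** The contradiction is real and should be fixed. Safety and Recording of Adverse Events limit the record to Grade 3+ events related to an undefined class of procedures; Risks to Participants puts every AE in the CRF. The content of the AE-based primary safety endpoint therefore depends on which section is followed and, if it is Safety, on whether the randomised drug counts as a procedure.

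The effect is on the completeness of descriptive safety reporting by arm. Its size cannot be computed, since the documents give no incidence, grade mix or attribution pattern. The conclusion assumes that the CRF is the source of the safety tables, as its role as main data instrument implies. It does not rest on any claim that limited AE collection is improper in itself.

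**What to change.** Reconcile Safety, Recording of Adverse Events and Risks to Participants to one collection rule, applied identically in both arms.

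- **Simplest course:** adopt the all-AE CRF rule already in Risks to Participants and delete the limit in Safety and the reference to it in Recording of Adverse Events. Record grade and relatedness as data fields, not as conditions of entry, and tabulate events by randomised arm.
- **If the sponsor keeps limited collection:** define study-mandated procedures, say whether the standard-of-care biopsies and the randomised drug are included, remove the all-AE CRF instruction, and restate the primary safety endpoints so that they claim only what is collected.

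The cost is protocol wording and, under the first course, additional CRF entry for 50 patients over 12 months. The volume cannot be estimated from the documents. No new visits are needed, because staff already ask about AEs at each contact and record all of them in source documents.

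### The safety section limits AE collection to Grade 3+ procedure-related events while the risk section puts all AEs in the CRF, and no by-arm AE summary is planned

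*Combined protocol and SAP*

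**What the plan says.** The Safety section defines the endpoint broadly: "The primary safety endpoints will be assessed on the AEs and SAEs that are observed throughout the trial". It grades all events by CTCAE and then narrows what is gathered: "The collection of AE's and SAE's is limited in this study to those Grade 3 or higher that are related to study mandated procedures".

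Two instructions appear under Recording of Adverse Events. The first is "Information on all adverse events will be recorded in the source document". The second points back to the restriction: "All adverse events occurring during the study period that meet the criteria above will be recorded". Each event is followed to resolution, to stabilization, or "until it has been determined that the study treatment or participation is not the cause".

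The section on risks to participants says that CTCAE "will be used to grade all adverse (either serious or non-serious) events". It continues: "Information on all adverse events (signs, symptoms, abnormal diagnostic procedures, treatments) will be recorded in the appropriate adverse event module" of the CRF. It adds: "Medical monitoring will include a regular assessment of the number and type of serious adverse events". Data Handling and Record Keeping makes the electronic CRF the main data collection instrument.

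Stopping Rules lists UTI, CMV, HSV, EBV, HCV, HBV, HIV and PCP as infections that may end a subject's participation. It calls them adverse events and remarks that fewer are expected in the experimental arm.

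In the Statistical analysis section, the clinical events with a stated analysis are acute rejection, graft failure or loss, and death.

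**The concern.** The trial compares two formulations of an immunosuppressant. The hypothesised benefit comes from avoiding under-immunosuppression, and fewer donor-reactive T cell clones count in favour of the new formulation. The harms that naturally sit beside that benefit are drug toxicity and non-fatal infection. The restriction is tied to procedures, whereas the arms differ in the drug. A safety endpoint collected under it could miss the events most relevant to the comparison.

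The plan also gives site staff two different instructions for the same CRF. What is recorded, and what the periodic review of SAEs sees, would depend on which instruction staff followed. Even a complete record would have no planned presentation by arm.

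**Working it through.** The plan states no figure on this point, so the main check compares the texts. The only arithmetic is the precision of the proposed table.

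**1. Which rules conflict?**

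| Section | What is recorded | Where |
|---|---|---|
| Safety | Grade 3+ and procedure-related only | study collection |
| Recording of Adverse Events, first paragraph | all AEs | source document |
| Recording of Adverse Events, second paragraph | AEs meeting the restriction | location not stated |
| Risks to participants | all AEs, serious or not | CRF adverse event module |

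The first-paragraph rule concerns source documents. It fits either a full or a restricted study dataset. The risk section names the CRF, so it cannot be reconciled with the Safety restriction in that way.

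**2. What does the restriction remove if followed?**
- All Grade 1-2 events go, whatever their cause.
- Events not related to procedures go at any grade, including SAEs, because the sentence covers both AEs and SAEs.
- Drug-related events probably go. Study-mandated procedures are not defined, and the risk section describes subjects' risks as those of venipuncture and biopsy passes, plus rejection. On the other side, the follow-up rule mentions study treatment as a possible cause. If the phrase were meant to include the assigned tacrolimus, Grade 3+ drug-related events would stay, but lower-grade or unrelated infections would still be lost.

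**3. Is there a by-arm summary?** The Statistical analysis section assigns logistic regression, Kaplan-Meier and Cox models to rejection, graft failure and death. Its general plan for univariate and bivariate analyses does not mention adverse events. The SAE review in the risk section names number and type, with no comparison by arm.

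**4. How precise would a by-arm table be?** Inputs: n = 25 per arm (Number of Participants). The infected proportions are assumptions, taken as equal in the two arms. With Wilson 95% limits l and u for each proportion p, the Newcombe interval for a zero difference has half-width √[(p − l)² + (u − p)²].

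| Infected per arm (assumed) | p | l | u | Half-width |
|---|---|---|---|---|
| 3/25 | 0.12 | 0.042 | 0.300 | √(0.078² + 0.180²) = 0.196 |
| 5/25 | 0.20 | 0.089 | 0.391 | √(0.111² + 0.191²) = 0.221 |
| 10/25 | 0.40 | 0.234 | 0.593 | √(0.166² + 0.193²) = 0.254 |
| 12/25 | 0.48 | 0.300 | 0.665 | √(0.180² + 0.185²) = 0.258 |

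The half-width runs from about 20 to 26 percentage points. Such a table can describe but cannot confirm or refute a difference.

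**The case against.** The strongest reply is that the Safety sentence is the specific rule for this study. Recording of Adverse Events refers back to it, and the risk section speaks of reporting events as already described, so its CRF sentence could be general wording. On that view, aligning one sentence in the risk section would remove the conflict. This is a 50-patient pilot of marketed drugs that the sponsor does not supply, with standard-of-care follow-up, and limited collection may be defensible. Both arms are titrated to troughs of 8-12 ng/ml, so a difference in infection is not obvious. The remark about fewer infections is a parenthesis and not a hypothesis. Source documents, and continued follow-up of withdrawn subjects, would allow later abstraction.

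Much of this stands. The conflict could be settled in either direction, and widening collection is a design choice. But settling it on the restricted rule would leave a declared primary safety endpoint without low-grade events and probably without drug-related ones. Later abstraction is less consistent than one prospective rule, particularly with open-label treatment. The general bivariate sentence does not commit the team to a safety table.

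A reader might infer that the source-document sentence also contradicts the restriction. It does not, because a complete source record is compatible with a narrower dataset. A reader might also infer that the listed infections will certainly be lost. The text shows only that their capture is not assured.

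**Conclusion.** The concern holds for one conflict and one omission. The Safety restriction, repeated in the second paragraph of Recording of Adverse Events, is incompatible with the CRF rule in the risk section. No adverse event or infection summary by arm is named. As written, the restriction excludes all Grade 1-2 events and, on the more likely reading of an undefined term, drug-related events.

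The number of events affected cannot be sized. It is tempting to assume infection counts and a share retained by the restriction and to present the resulting drop as the effect of choosing one rule. The documents give neither the infection rates nor the share, so such a drop would only reflect the assumptions. The intervals in the working show the precision of the proposed table, under assumed equal proportions of 12% to 48%. They are not evidence of harm or bias.

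The primary graft-function and immune endpoints are unaffected, as are the analyses of rejection, graft loss and death. The change should be made because the safety dataset is otherwise not clearly defined and the correction is cheap.

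**What to change.** 1. **Safety and Recording of Adverse Events.** Replace the limiting sentence, and delete the qualifier in the second paragraph that refers back to it, so that one rule matching the risk section applies. Adverse events are recorded in the CRF in both arms to 12 months post-transplant, regardless of relation to procedures. The minimum set is all SAEs, all Grade 3+ AEs, and all infections on the Stopping Rules list at any grade, with type, CTCAE grade and onset date. Include infections that lead to study exit and those found during follow-up after withdrawal. If only this minimum is adopted, word the risk section to match.
2. **Statistical analysis.** Add one descriptive table by assigned arm: patients with any SAE, any Grade 3+ AE and any listed infection, with counts, proportions, and the risk difference with its 95% CI. No test.
3. **Stopping Rules (optional, editorial).** Remove the remark that fewer infections are expected, or label it as untested.

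The cost is a few wording edits, an infection entry in the CRF module already described, and a small amount of extra recording for 50 patients, including those withdrawn. Intervals will be wide, as shown in the working. Because treatment is open label, mild events may be noted unevenly between arms, so the table should be read as descriptive.

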### **Recording of Adverse Events**

At each contact with the subject, the investigator/member of investigator's team will seek information on adverse events by specific questioning and, as appropriate, by examination. Information on all adverse events will be recorded in the source document. All clearly related signs, symptoms, and abnormal diagnostic procedures results should be recorded in the source document, though should be grouped under one diagnosis.

All adverse events occurring during the study period that meet the criteria above will be recorded. The clinical course of each event should be followed until resolution, stabilization, or until it has been determined that the study treatment or participation is not the cause. Serious adverse events that are still ongoing at the end of the study period must be followed up to determine the final outcome. Any serious adverse event that occurs after the study period and is considered to be possibly related to the study treatment or study participation will be recorded and reported according to IRB requirements.

